### 9.1.2.2 Secondary

- Proportion of patients who remain relapse-free in each year and at 4 and 5 years after initiation of cladribine tablet treatment
- Time from cladribine tablet initiation to first relapse
- Proportion of patients who discontinued cladribine tablets and reasons for discontinuation
- Subsequent DMTs (none or by DMT type) received after cladribine tablets discontinuation/treatment completion up to 5 years after cladribine tablets initiation
- Disability assessed by the EDSS at treatment initiation and start of treatment Year 2

The EDSS is a neurological assessment to evaluate disability in patients with MS, performed by the physician. The annual EDSS at cladribine tablet treatment initiation and start of treatment Year 2 will be recorded, where available in the patients' notes. EDSS is routinely collected as part of standard care in the UK as part of the annual assessment required for continuation of treatment.

- Proportion of patients with disability progression confirmed over 6 months, assessed by the EDSS, at 2 years after cladribine tablet treatment initiation

An EDSS progression is defined as an increase in the EDSS scale as follows:

- If the EDSS score at cladribine tablet initiation is 0, the increase must be  $\geq 1.5$  units
- If the EDSS score at cladribine tablet initiation is  $\geq 0.5$  or  $\leq 4.5$ , the increase must be  $\geq 1.0$  units
- If the EDSS score at cladribine tablet initiation is  $\geq 5.0$ , the increase must be  $\geq 0.5$  units.

A confirmed disability progression is defined as EDSS progression (as defined above) confirmed after 6 months.

- Rates of selected, identified, and potentially clinically important AEs, including:

- grade 3 lymphopenia
- grade 4 lymphopenia
- herpes infections
- serious infections (infections for which a hospitalisation is initiated or extended)
- opportunistic infections (new onset or reactivation of latent infection)
- malignancies

These AEs will be reported from the date of cladribine tablet initiation and will be described overall and by most recent prior DMT subgroups (DMT naïve, prior platform treatment, prior high-efficacy cell-depleting treatment, and prior high-efficacy non-depleting treatment).

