- Selected adverse events: Reporting of AEs once informed consent has been obtained (as described in [Section 11](#)), with special focus on:
  - grade 3 lymphopenia
  - grade 4 lymphopenia
  - herpes infections
  - serious infections (infections for which a hospitalisation is initiated or extended), opportunistic infections (new onset or reactivation of latent infection)
  - malignancies.

For each AE, the start date, end date, classification of serious or non-serious, and outcome should be reported.

Derived and transformed data needed for the analysis are described in [Section 9.7.2](#).

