## 11 Adverse Events

### 11.1 Definitions

An AE is any untoward medical occurrence in a patient or clinical study subject administered a pharmaceutical product and which does not necessarily have a causal relationship with this treatment. An AE can therefore be any unfavourable and unintended sign (including an abnormal laboratory finding), symptom, or disease temporally associated with the use of a medicinal product, whether or not considered related to the medicinal product.

Investigators should assess the severity/intensity of any AE as follows:

**Mild:** The subject is aware of the event or symptom, but the event or symptom is easily tolerated.

**Moderate:** The subject experiences sufficient discomfort to interfere with or reduce his or her usual level of activity.

**Severe:** Significant impairment of functioning: the subject is unable to carry out usual activities.

A serious adverse event is any AE as defined above, which also fulfils at least one of the seriousness criteria below:

- Results in death
- Is life-threatening
- Requires in-patient hospitalisation or prolongation of existing hospitalisation
- Results in persistent or significant disability/incapacity
- Is a congenital anomaly/birth defect
- Is otherwise considered as medically important

 Life-threatening in this context refers to a reaction in which the patient was at risk of death at the time of the reaction; it does not refer to a reaction that hypothetically might have caused death if more severe.

 Medical and scientific judgement should be exercised in deciding whether other situations should be considered as serious reactions, such as important medical events that might not be immediately life-threatening or result in death or hospitalisation but might jeopardise the patient or might require an intervention to prevent one of the other outcomes listed above. Such important medical events should be considered as serious.

Examples of such events are intensive treatment in an emergency room or at home for allergic bronchospasm, blood dyscrasias or convulsions that do not result in hospitalisation or development of dependency or abuse. As a guidance, the important medical event terms list is intended to be used for assessment of suspected adverse reactions (see EMA/207865/2017).

---

Any suspected transmission via a medicinal product of an infectious agent is also considered a serious adverse reaction.

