15.1.1 All Adverse Events

The AEs will be summarised using the latest version of MedDRA PT as event category and MedDRA primary SOC body term as body system category.

Incomplete AE-related dates will be handled as specified in Section 9.10.

The following tables will be created:

- TEAE summary table with the number and percentage of patients that have:
 - TEAE
 - TEAE of Special Interest (TEAESI)
 - Grade 3 Lymphopenia
 - Grade 4 Lymphopenia
 - Herpes infections
 - Serious/opportunistic infections
 - Malignancies
 - TEAE leading to death

- TEAE leading to cladribine dose reduction
- TEAE leading to cladribine dose increase
- TEAE leading to cladribine temporary interruption
- TEAE leading to cladribine permanent discontinuation
- TEAE not recovered/resolved
- Any serious TEAE:
 - TEAESI
 - Leading to death
 - Leading to cladribine dose reduction
 - Leading to cladribine dose increase
 - Leading to cladribine temporary interruption
 - Leading to cladribine permanent discontinuation
 - Not recovered/resolved
- Cladribine-related TEAE:
 - TEAESI
 - Serious
 - Leading to death
 - Leading to cladribine dose reduction
 - Leading to cladribine dose increase
 - Leading to cladribine temporary interruption
 - Leading to cladribine permanent discontinuation
 - Not recovered/resolved
- The number and percentages of patients with TEAE by Primary SOC and PT
- The number and percentages of patients with TEAESI by Primary SOC and PT
- The number and percentages of patients with serious TEAE by Primary SOC and PT
- The number and percentages of patients with TEAE related to cladribine by Primary SOC and PT

TEAESI will be individuated using standardized and/or customized MedDRA queries that will be shared by Merck safety department using the dictionary version available at the time of the final analysis data-cut.

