15.2 Clinical Laboratory Evaluation

Baseline Lymphocytes results and highest and lowest change from baseline (cladribine initiation) will be summarised. Only the most extreme (lowest and highest) post-baseline Lymphocytes assessments will be retained in the analysis and used for the lowest and highest change from baseline analyses respectively. In case only one post-baseline result is available, it will be used for both analyses.

Lymphocytes results will be summarised descriptively and change from baseline will be calculated if available. In addition, lymphocytes counts will be classified by grade as follows (Fisher et al., 2017):

- Normal lymphocyte level: $\geq 1.0 \text{ } 10^9/\text{L}$ (lower level of normal)
- Grade 1: $0.8 \text{ to } <1.0 \text{ } 10^9/\text{L}$
- Grade 2: $0.5 \text{ to } <0.8 \text{ } 10^9/\text{L}$
- Grade 3: $0.2 \text{ to } <0.5 \text{ } 10^9/\text{L}$
- Grade 4: $<0.2 \text{ } 10^9/\text{L}$

Lymphocytes will be displayed in $10^9/\text{L}$ unit.

Results reported in other units will be converted as follow:

$$10^9/\text{L} = \text{Cells/mm}^3/1000$$

$$10^9/\text{L} = \text{Cells}/\mu\text{L}/1000$$

$$10^9/\text{L} = 10^3/\text{mm}^3$$

$$10^9/\text{L} = \text{K}/\mu\text{L}$$

$$10^9/\text{L} = \text{K}/\text{mm}^3$$

$$10^9/\text{L} = \text{Gpt/L}$$

Results reported in other units will not be converted. All results will be displayed in a listing in their original units.

16 Other Outcome MRI Lesions

This analysis will be performed based on the FAS.

16.1 Other Outcome MRI Lesions: Derivation and analysis of the Other Outcome MRI Lesions

The number % of patients with the following lesions (as recorded in the MRI CRF page) will be summarised in a table:

- T1 gadolinium enhancing lesions
- T2 lesions (new)
- T2 lesions (enlarging)

All data collected on the MRI CRF page will be listed.

17

References

ICH E3 Structure and Content of Clinical Study Reports (Step 5, July 1996)

ICH E3 Structure and Content of Clinical Study Reports: Questions and Answers (R1) (January 2013)

ICH E9 Statistical Principles for Clinical Trials (Step 4, February 1998)

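### SAP 15.1.1 gives no rule for assigning Grade 3 or Grade 4 lymphopenia and does not link those rows to the count-based grades in SAP 15.2

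*SAP*

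**What the plan says.** - **Outcome.** Protocol 9.1.2.2 defines the outcome as "Rates of selected, identified, and potentially clinically important AEs, including" a list whose first two items are grade 3 lymphopenia and grade 4 lymphopenia.
- **Identification.** SAP 15.1.1 lists both grades under the special-interest line of the TEAE summary table and states that "TEAESI will be individuated using standardized and/or customized MedDRA queries". The section gives no grading rule and does not point to SAP 15.2.
- **Severity.** Protocol 11.1 says "Investigators should assess the severity/intensity of any AE as follows" and then gives mild, moderate and severe. Severe is defined as "Significant impairment of functioning: the subject is unable to carry out usual activities".
- **AE items.** Protocol 9.3 says "For each AE, the start date, end date, classification of serious or non-serious, and outcome should be reported". Grade is not in that list.
- **Counts.** Protocol 9.3 collects lymphocyte levels at initiation and afterwards, where available. In SAP 15.2, "lymphocytes counts will be classified by grade as follows": Grade 3 is 0.2 to <0.5 and Grade 4 is <0.2 (10^9/L). The lowest and highest post-baseline values per patient are retained. The section does not explicitly ask for the number and percentage of patients by worst grade.
- **Denominator.** By default, SAP 9 bases proportions on the whole analysis set, with missing observations as their own category.

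**The concern.** Grades 3 and 4 are defined by a laboratory count, but SAP 15.1.1 builds their rows from coded AE terms. A coded term says that lymphopenia was recorded, not how low the count was. The severity scale describes symptoms and function, and its top level does not split into two grades.

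Lymphopenia is one of the two adverse reactions that Protocol 7.2 singles out as most common and clinically relevant, and Protocol 7.3 calls its real-world occurrence an open question. If the rows rest on AE entries, the reported rates depend partly on how readily each site enters a laboratory value as an AE. That can also distort the description by prior-DMT subgroup. The report could then carry two different Grade 3 figures, one from 15.1.1 and one from 15.2, with nothing to say which is the outcome.

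**Working it through.** The documents state no expected lymphopenia rate, so there is no figure to reproduce. The check traces the text and follows example patients through both sections.

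**1. Can the 15.2 bands supply the grade?** Applying the cut-offs (10^9/L) at and just below each boundary:

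| Count | Class |
|---|---|
| 1.0 | Normal |
| 0.99, 0.8 | Grade 1 |
| 0.79, 0.5 | Grade 2 |
| 0.49, 0.2 | Grade 3 |
| 0.19 | Grade 4 |

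The bands are contiguous and do not overlap. Every count in a convertible unit gets exactly one grade, and because the lowest post-baseline value is kept, a worst grade per patient can be derived.

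**2. Example patients under each section as written**

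| Patient | SAP 15.1.1 rows | SAP 15.2 |
|---|---|---|
| Charted count 0.4, no AE entry | Not an event | Grade 3 (0.2 ≤ 0.4 < 0.5) |
| AE coded as lymphopenia, no grade in the record | Found by query; no rule places it in either row | Graded if a usable count exists |
| AE record that states the grade, no usable count | An event if the grade is read from the record, which the SAP does not specify | Missing |
| No count and no AE entry | Event-free, but in the denominator | Missing |

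The two sections can disagree in both directions, and the SAP sets no precedence.

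**3. Size of an under-count, under assumptions only.** Let N be the number of patients, p the true share with a count-defined Grade 3 or 4 event, and f the share of those entered as AEs. The AE rows then show N × p × f patients. N comes from Protocol 9.5 (minimum 90, about 200 planned). The documents give neither p nor f.

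- N = 90, p = 10%: 90 × 0.10 = 9 true cases. With f from 25% to 100%, the rows show 9 × 0.25 = 2.25 (about 2) to 9.
- N = 200, p = 10%: 200 × 0.10 = 20 true cases. The rows show 20 × 0.25 = 5 to 20.
- N = 90 with p from 5% to 25%: from 90 × 0.05 × 0.25 = 1.1 to 90 × 0.25 × 1.00 = 22.5.

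At f = 100% there is no under-count. The range shows how far the result depends on an unknown; it is not an estimate.

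**4. Denominator.** If m of N patients have no count and x of the others are cases, a row over the full set shows x/N, whereas the proportion among tested patients is x/(N − m). The first is smaller by the factor (N − m)/N. The documents do not give m.

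**The case against.** A reader might infer that the two outcomes cannot be derived at all, or that the AE rows will certainly miss cases. The documents do not support either reading.

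- The AE item list in Protocol 9.3 is not exhaustive. It also omits severity, relationship and action taken with cladribine, all of which SAP 15.1 and 15.1.1 use. The eCRF is not shown, so a grade field cannot be ruled out, and the list does not prove that grade is uncollected.
- Protocol 9.3 provides for "Reporting of AEs once informed consent has been obtained" with special focus on these two graded events, so a site may write the grade into the reported term, and a customized query might use it.
- The AE definition in Protocol 11.1 covers any unfavourable sign, "including an abnormal laboratory finding), symptom, or disease temporally associated with the use of a medicinal product". Protocol 11.2 has any AE abstracted regardless of seriousness, and Protocol 3.1 makes the investigator responsible for recording laboratory abnormalities. A low count left off the AE page would be a site omission that the plan does not prescribe.
- SAP 15.2 already grades the counts, a deliberate addition in version 3.0. A patient at 0.4 with no AE entry would appear in that listing and probably in its summary.
- The protocol defines the outcome as rates of AEs. A purely laboratory row would change that definition, would depend on testing frequency, and would lose AE-documented cases with no usable count.

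These points stand. They limit the claim to rows that may miss cases, and they shape the fix. They do not supply the missing rule: no text says that a reported grade or an eCRF field fills the rows, or that 15.2 feeds them.

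**Conclusion.** The gap is real but narrower than a first look suggests. As written, SAP 15.1.1 contains no rule that turns a query-identified AE into Grade 3 or Grade 4. The one AE intensity scale in the documents cannot provide it, and the count-based grades in 15.2 are not connected to the rows. The rows may miss count-defined cases not entered as AEs, may conflict with the 15.2 output, and count patients who have neither a lymphocyte count nor an AE entry as event-free.

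The size cannot be determined from the documents, because the true rate, the share of low counts entered as AEs and the number of patients without counts are all unstated. The conclusion assumes that no unseen document, such as the eCRF or the query specification, sets the grading rule. The study is descriptive and tests no hypothesis, this is a secondary outcome, and the data needed are already collected. The point is therefore one that should be fixed, and it does not invalidate the plan.

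**What to change.** In SAP 15.1.1:

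1. Derive the Grade 3 and Grade 4 rows from each patient's lowest post-initiation lymphocyte count, using the 15.2 cut-offs. A baseline value is not needed for this.
2. Report n (%) among patients with at least one usable post-initiation count, and state the number with none, overall and by prior-DMT group. Results in units that 15.2 does not convert count as not usable.
3. Show AE-reported lymphopenia as a separate row, with the grade where the record gives it.
4. Report the cases found in only one source, so that AE-documented cases without a usable count are not lost.
5. Cross-refer 15.1.1 and 15.2, and record the change in SAP 7, which now declares no departure from the protocol's planned analyses.

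While editing 15.2, reconcile the year cited for the grading source (2017) with the reference list (2021).

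The cost is SAP wording and a derived variable from data already in the eCRF. The count-based rate will depend on how often patients are tested in routine care, and the reported lymphopenia rates may be less favourable.

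### The SAP's merged, query-based infection row does not give the protocol's serious-infection outcome, which is defined by hospitalisation

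*SAP*

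**What the plan says.** Protocol 9.1.2.2 lists among the selected adverse events "serious infections (infections for which a hospitalisation is initiated or extended" and, as its own bullet, "opportunistic infections (new onset or reactivation of latent infection". The abstract and Protocol 9.3 repeat both definitions.

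On data items, Protocol 9.3 states: "For each AE, the start date, end date, classification of serious or non-serious, and outcome should be reported". Protocol 11.1 classes an event as serious if it is an AE "which also fulfils at least one of the seriousness criteria below". There are six criteria. One is "Requires in-patient hospitalisation or prolongation of existing hospitalisation"; another is "Is otherwise considered as medically important".

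In the SAP, the summary table in 15.1.1 has a single TEAESI row, "Serious/opportunistic infections". The method for all TEAESI is that "TEAESI will be individuated using standardized and/or customized MedDRA queries", with the queries to come from the sponsor's safety department. The section also plans a table of serious TEAEs by SOC and PT, and a TEAESI line under the heading for any serious TEAE. SAP section 7 reports no departures from the protocol's planned analyses.

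**The concern.** The protocol's outcome depends on what happened to the patient (a hospital stay began or was extended). The SAP's rule depends on which term was coded. The same infection term can describe an illness managed at home or in hospital, so no term list can apply the definition. The merged row adds a second problem: two outcomes with different definitions share one count and cannot be separated afterwards.

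At stake is a named secondary safety outcome for a lymphocyte-depleting drug, in a study whose rationale (Protocol 7.3) calls real-world safety an open question for UK clinicians. Because section 7 declares no change, a reader of the report would take the row for the protocol's outcome.

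**Working it through.** No sample size, rate or test is involved, so the check sets the rules side by side.

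**Inputs**
- Target: infection with hospitalisation started or extended (Protocol 9.1.2.2).
- SAP row: TEAEs whose term is in the query, serious and opportunistic together (SAP 15.1.1).
- Serious flag: any one of six criteria suffices, and hospitalisation is one of them (Protocol 11.1).
- Events available: Protocol 11.2 has AEs abstracted whatever their seriousness, so infections managed at home are in the data too.

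**How each rule treats an infection**

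| Infection event | Protocol outcome | SAP row as written | Serious flag |
|---|---|---|---|
| Hospitalised, term in query | counted | counted | counted |
| Hospitalised, term not in query | counted | missed | counted |
| Not hospitalised, serious for another reason, term in query | not counted | counted | counted |
| Not hospitalised, not serious, term in query | not counted | counted | not counted |
| Opportunistic, not hospitalised, term in query | not counted (separate outcome) | counted | only if serious for another reason |

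**What follows**
1. Neither set contains the other when the SAP row is compared with the protocol outcome. The row can be too high or too low, depending on how the query list is drawn.
2. Since hospitalisation is itself a seriousness criterion, every hospitalised infection should carry the serious flag. Patients with a serious TEAE in the infections SOC therefore include all who meet the protocol definition, plus any whose infection was serious under one of the other five criteria (6 − 1 = 5). That count is an upper bound, provided the flag is complete and the infections are coded to that SOC.
3. The TEAESI line under any serious TEAE does not help. It pools infections with lymphopenia and malignancy.
4. No planned table therefore reports the serious-infection outcome as the protocol defines it.

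**The case against.** The strongest reply is that the query is unlikely to be the only filter. The same TEAESI list has rows for grade 3 and grade 4 lymphopenia, and grade is an attribute of the event rather than part of the diagnosis. The infection row itself carries the word serious. Queries may be meant to pick the topic, with recorded attributes completing the row. This is plausible, but the SAP does not say it. Even if it were so, the attribute would be the six-criterion flag, not hospitalisation, and opportunistic infections would still be merged in.

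A second reply is that the serious-TEAE table by SOC and PT does not depend on the query, so it would show a hospitalised infection that the query missed. This stands, and it limits the harm: for that table the remaining error runs only upward.

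Third, Protocol 9.3 puts the two infection types on one line, which may explain the merged row. Each still keeps its own definition there, and 9.1.2.2 lists them separately.

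A reader might go further and infer that the outcome cannot be counted as defined, because the AE items listed in Protocol 9.3 include no hospitalisation item. The documents do not support that. The list is evidently not the whole AE form: severity (Protocol 9.7.3 and 11.1), relationship to treatment (SAP 15.1) and action taken on cladribine (SAP 15.1.1) are all used but not listed. Protocol 9.3 also names the hospitalisation definition itself just above that list. The eCRF is not among the documents, so it may hold the item.

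Finally, the study is descriptive and tests no hypothesis. That lowers the stakes for inference, but not the need to report an outcome under its own definition.

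**Conclusion.** The point holds as a gap in the analysis specification. As written, the SAP row does not give the protocol's serious-infection outcome, for two reasons: no rule applies the hospitalisation definition, and a second outcome is merged into the row. The serious-TEAE table gives an upper bound only. The discrepancy with the protocol is undeclared.

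No size can be attached. The documents give neither the frequency of infections, nor the share that led to hospital stays, nor the content of the queries. Any numerical contrast would rest on invented rates. The upper-bound statement assumes a complete serious flag and coding of infections to the infections SOC. Whether the hospitalisation item was collected is unknown. The change should be made, because without it the reported figure depends on a query list that the SAP does not specify.

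**What to change.** In SAP 15.1.1:
- Define serious infection as an AE in the MedDRA infections SOC **and** with hospitalisation initiated or prolonged.
- Give opportunistic infections a separate row, and state that a hospitalised opportunistic infection counts in both.
- Keep MedDRA queries for herpes infections, opportunistic infections and malignancies.

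Before database lock, confirm that the AE form records hospitalisation or the seriousness criterion that was met. If it does not, report infection AEs flagged serious, label the figure as an upper bound that differs from the protocol definition, and list the difference in SAP section 7.

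Cost: a few lines of SAP text, one extra table row and a check of the AE form. SAP version 3.0 is dated 12 September 2023 and lock is planned for Q4 2023, so the wording can still be changed in time on that schedule. The fallback needs no new data, which avoids going back to charts at the 7 or 8 sites.
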